9.1.2.2 Procedures and analysis

Given the potential effects of navitoclax on platelets and bleeding risk, platelet count and coagulation studies (INR, PTT) will be checked on the same day prior to any research biopsies performed while patient is taking study drugs. A platelet count of >50,000/m³ and an INR and PTT in the normal/acceptable range according to institutional guidelines will be required for a patient to undergo tumor biopsy.

Pre-treatment biopsies will be obtained between days -21 and -1 of treatment. When possible, it is preferred, but not required, that the pre-treatment biopsy be performed between days -7 and -1 of treatment in order to most accurately represent the baseline signaling activity prior to treatment. On-treatment biopsies will be obtained after ~2 weeks of combination dosing (day 22 +/- 7 days for Schedule A dosing, day 15 +/- 7 days for Schedule B or C dosing). Core biopsies of the same tumor lesion will be obtained at each time point. A minimum of one core will be formalin-fixed and paraffin-embedded, and a minimum of one core will be flash frozen. Both formalin-fixed paraffin-embedded and flash frozen tissue will be stored in the pathology department at the Massachusetts General Hospital.

Paired biopsies will be used to assess the pharmacodynamic response to therapy in patients treated with trametinib and navitoclax. Markers to be assessed will include proteins or mRNAs involved in MAPK or BCL2 family signaling (e.g. phospho-ERK, phospho-S6, or MAPK phosphatases such as DUSP6/MKP1) to evaluate pathway inhibition, markers of tumor cell proliferation (e.g. Ki67), and markers of apoptosis and cell death (e.g. Cleaved caspase-3).

These ancillary/exploratory analyses will be conducted in the Massachusetts General Hospital Molecular Pathology Biomarker Laboratory. For each patient, the change in marker level between the pre-treatment and on-treatment biopsies will indicate the effects of treatment on each marker. Results will be reported as a % increase or decrease in level of a given marker after treatment initiation (on-treatment biopsy) relative to before treatment (pre-treatment biopsy).

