Trial M06-814: Peak concentration was observed approximately 9 hours after dosing, with a terminal plasma half-life ($t_{1/2}$) of approximately 17 hours, with first-order elimination kinetics (Wilson *et al.*, 2010). Exposure was dose-proportional over a range of 10 mg/day to 440 mg/day, with an interpatient variability in exposure of 40%. The dose-normalized C_{max} and AUC_{0-24} of a non-fasting dose was about 20% higher than a fasting dose among subjects in the 10 mg through 440 mg cohorts. Dosages \geq 315 mg/day met the minimum plasma exposure predicted to be in the therapeutic range based on animal models. After a fasting dose, the oral clearance of navitoclax averaged about 4.4 L/h across all dose levels (Investigator's Brochure, 2011). Navitoclax was not detected in urine, indicating little to no renal excretion.

Trial M06-822: Peak concentration was observed approximately 7 hours after dosing, with a $t_{1/2}$ of approximately 15 hours (Gandhi *et al.*, 2011). Exposure (C_{max} and AUC_{0-24}) was dose-proportional over a range of 10 mg/day to 475 mg/day. Interpatient variability in dose-normalized C_{max} and AUC_{0-24} was about 40%, and values were similar between fasting and non-fasting conditions. Peak-to-trough plasma concentration ratio was close to twofold at steady state. Dosages \geq 225 mg/day met the minimum plasma exposure predicted to be in the therapeutic range based on animal models.

Trial M06-873: Peak concentration was observed approximately 6-8 hours after dosing in both the intermittent and continuous dosing cohorts (Roberts *et al.*, 2012). Exposure was dose-proportional over a range of 10 mg/day to 250 mg/day in the intermittent cohort, and interpatient variability in AUC was 46% for intermittent and continuous cohorts. No consistent trend was observed in dose-normalized steady-state trough concentrations over time. Navitoclax exposure did not demonstrate any correlation with age, sex, body weight, body surface area, renal function, or total bilirubin levels.

Clinical Efficacy

Trial M06-814: Overall, 21 of 46 patients with assessable adenopathy showed some reduction in tumor size (Wilson *et al.*, 2010). Ten of these patients achieved a PR of at

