Biopsies from patients in the Phase Ib portion of the trial will provide an evaluation of the effects of each cohort's dose level on signaling pathway inhibition, inhibition of tumor cell proliferation, and induction of tumor cell death. This will provide an important metric as to the extent of target inhibition at each given dose level. Paired biopsies obtained from the first 15 patients enrolled in the Phase 2 portion of the trial (minimum of 4 patients from each of cohorts 1, 2 and 3 will be biopsied) will provide a more detailed assessment of the pharmacodynamic effects of therapy at the RP2D and will offer the potential to correlate pharmacodynamic effects with tumor response and patient outcome.

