To reduce the incidence of significant thrombocytopenia associated with navitoclax dosing, a 7-day lead-in dosing period will be used for dose levels in which the target dose of navitoclax is greater than 150 mg daily (dose levels 3-7). Subjects will begin with navitoclax dosed at 150 mg PO daily and will escalate to the navitoclax dose defined in the cohort dose level after the 7th day of lead-in dosing if the subject's platelet count is ≥50,000/mm³ and the patient has no evidence of clinically significant bleeding, defined as grade 2 or higher hemorrhage regardless of platelet count. If the subject's platelet count on the 7th day of lead-in dosing is <50,000mm³, then the dose of navitoclax will be maintained at 150 mg daily for an additional 7 days. If the platelet count is <50,000mm³ after 14 days at the lead-in dose, then the lead-in dose will become the subject's dose for the duration of the study.

Two different schedules relating to the lead-in dosing period will be evaluated during Part 1 of this study. Schedule A will administer the 7-day lead-in dosing period of navitoclax as a single agent, prior to the initiation of trametinib dosing. Schedule B will begin the 7-day lead-in dosing period of navitoclax simultaneously with the initiation of trametinib dosing. Since potential drug interactions between trametinib and navitoclax are not yet defined, and since it is not yet known

Version Date: July 22, 2022

whether trametinib might potentiate the thrombocytopenia associated with navitoclax dosing, Schedule A (single agent lead-in) provides a potentially safer avenue for initial investigation of this combination. However, since navitoclax has not exhibited convincing single agent activity in pre-clinical models of KRAS mutant cancers ([name] et al., 2013), while trametinib has demonstrated activity in patients with KRAS mutant cancers (Infante et al, 2010; Messersmith et al., 2011), Schedule B may be preferable from an efficacy standpoint, as it does not delay the initiation of trametinib. Therefore, it will be important to determine if any meaningful differences in safety and tolerability exist between Schedules A and B. Schedule C (alternative dosing schedule with intermittent trametinib dosing) will be evaluated if unacceptable toxicity is observed during dose escalation on Schedules A or B. Schedules A, B and C are outlined below:

Schedule A Cycle 1 ONLY

Treatment day:

110	uuii	CIIt	uu.	, •																							

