1	2	3	4	5	6	7	8	9	10	11	12	13	14	15	16	17	18	19	20	21	22	23	24	25	26	27	28
							Т	T	Т	Т	Т	Т	T	Т	T	T	T	Т	Т	Т	Т	Т	T	Т	T	T	Т
L	L	L	L	L	L	L	N	N	N	N	N	N	N	N	N	N	N	N	N	N	N	N	N	N	N	N	N

Cycle 2 and Subsequent Cycles

Treatment day:

1	2	3	4	5	6	7	8	9	10	11	12	13	14	15	16	17	18	19	20	21	22	23	24	25	26	27	28
Т	Т	Т	Т	T	T	T	T	T	T	T	T	Т	T	T	T	T	T	T	T	T	T	T	Т	Т	T	T	Т
N	N	N	N	N	N	N	N	N	N	N	N	N	N	N	N	N	N	N	N	N	N	N	N	N	N	N	N

Schedule B Cycle 1 ONLY

Treatment day:

				/																							
1	2	3	4	5	6	7	8	9	10	11	12	13	14	15	16	17	18	19	20	21	22	23	24	25	26	27	28
Т	Т	Т	T	Т	Т	Т	T	T	Т	T	Т	Т	Т	Т	T	Т	Т	Т	Т	Т	Т	Т	T	Т	T	Т	Т
L	L	L	L	L	L	L	N	N	N	N	N	N	N	N	N	N	N	N	N	N	N	N	N	N	N	N	N

Version Date: July 22, 2022

Cycle 2 and Subsequent Cycles

Treatment day:

1	2	3	4	5	6	7	8	9	10	11	12	13	14	15	16	17	18	19	20	21	22	23	24	25	26	27	28
Т	Т	Т	Т	Т	Т	Т	Т	Т	Т	T	Т	Т	Т	Т	T	T	T	Т	T	Т	T	Т	Т	Т	T	Т	Т
N	N	N	N	N	N	N	N	N	N	N	N	N	N	N	N	N	N	N	N	N	N	N	N	N	N	N	N

Schedule C Cycle 1 ONLY

Treatment day:

1	2	3	4	5	6	7	8	9	10	11	12	13	14	15	16	17	18	19	20	21	22	23	24	25	26	27	28
Т	T	Т	Т	Т	Т	Т	Т	Т	Т	Т	Т	Т	Т														
L	L	L	L	L	L	L	N	N	N	N	N	N	N	N	N	N	N	N	N	N	N	N	N	N	N	N	N

Cycle 2 and Subsequent Cycles

Treatment day:

1	2	3	4	5	6	7	8	9	10	11	12	13	14	15	16	17	18	19	20	21	22	23	24	25	26	27	28
T	T	T	Т	Т	T	T	Т	T	T	Т	T	Т	Т														
N	N	N	N	N	N	N	N	N	N	N	N	N	N	N	N	N	N	N	N	N	N	N	N	N	N	N	N

T = trametinib dose defined by Phase 1b dose level or RP2D

L = lead-in dose of navitoclax (150 mg daily).

N = Navitoclax dose defined by Phase 1b dose level or RP2D. Note: as described above, after 7 days of navitoclax at the lead-in dose of 150 mg daily (L), dose will be escalated to the dose defined by the Phase 1b dose level or the RP2D (A), only if subject's platelet count is ≥50,000/mm³ and the patient has no evidence of clinically significant bleeding, defined as grade 2 or higher hemorrhage regardless of platelet count. If the subject's platelet count on the 7th day of lead-in dosing is <50,000mm³, then the dose of navitoclax will be maintained at 150 mg daily for an additional 7 days. If the platelet count is <50,000mm³ after 14 days at the lead-in dose, then the lead-in dose will become the subject's dose for the duration of the study.

Evaluation of dosing Schedules A and B will be performed according to the schema in **Figure 5.1.** Since it is not yet known whether drug interactions might occur between trametinib and

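### For Schedules B and C above 150 mg navitoclax, the on-treatment biopsy window opens with no completed day at the assigned navitoclax dose, yet the result is read as the effect of that dose

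*Combined protocol and SAP*

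**What the plan says.** Section 9.1.2.2 sets the aim and the two windows: "On-treatment biopsies will be obtained after ~2 weeks of combination dosing", with "day 22 +/- 7 days for Schedule A dosing" and "day 15 +/- 7 days for Schedule B or C dosing".

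The dosing grids in Section 5.1.1 give navitoclax as L on days 1-7 and N from day 8, where "L = lead-in dose of navitoclax (150 mg daily". Their note says that "after 7 days of navitoclax at the lead-in dose of 150 mg daily (L), dose will be escalated", provided platelets are at least 50,000/mm³ and there is no clinically significant bleeding. If day-7 platelets are below 50,000/mm³, 150 mg is kept for another 7 days. If they are still below after 14 days, 150 mg becomes the patient's dose for the rest of the study. Section 5.1.2 repeats these rules for Part 2. Table 5.1 limits the lead-in to levels 3-7; levels 1-2 are 150 mg throughout.

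On biopsy days, navitoclax is taken in the morning at least two hours before the procedure (Section 5.1). A research biopsy on study drug needs platelets above 50,000 (Section 9.1.2.2) that are also stable (Section 9.1.2.3).

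On interpretation, Section 2.5.2 says of the Part 1 biopsies: "This will provide an important metric as to the extent of target inhibition at each given dose level". Section 9.1.2.1 repeats this and gives the Part 2 biopsies the same role for the RP2D. Section 13.4.1.3 reports percent change at the day 15 biopsy. No section requires a minimum time at the assigned navitoclax dose, or ties the result to the actual biopsy day or the dose taken.

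**The concern.** The purpose of the paired biopsies is to learn how much pathway inhibition and apoptosis a given dose level produces. A biopsy at the opening of the B/C window meets the protocol while saying little about the assigned navitoclax dose. With 3 to 6 patients per level, one such pair is between a sixth and a third of the evidence for that level. The direction is predictable: early-edge samples pull higher levels towards the 150 mg result and weaken any dose-effect relation.

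The gap in exposure could matter biologically. In the navitoclax study in small-cell lung cancer and other solid tumors (Section 2.2.2), doses of 225 mg/day and above reached the minimum plasma exposure predicted to be therapeutic. The lead-in is below that figure and levels 5-7 are above it.

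Schedule C is the one most exposed, because Section 5.1.1 ends further escalation on Schedules A and B from protocol Version 10.

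**Working it through.** **Inputs.** Windows: Section 9.1.2.2. Dosing days: Section 5.1.1 grids. Navitoclax half-life 15-17 h, peak at 6-9 h, dose-proportional exposure, interpatient variability about 40%: Section 2.2.2. Trametinib half-life 4.5 days: Section 2.2.1.2.

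**1. Completed dosing days before the biopsy (patient escalated on day 8).**

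| Schedule, biopsy day | Trametinib days | Navitoclax 150 mg days | Navitoclax assigned-dose days |
|---|---|---|---|
| A, day 15 (opens) | 7 | 7 | 7 |
| A, day 22 (nominal) | 14 | 7 | 14 |
| B or C, day 8 (opens) | 7 | 7 | **0** |
| B or C, day 15 (nominal) | 14 | 7 | 7 |
| B, day 22 (closes) | 21 | 7 | 14 |
| C, day 22 (closes) | 14, then 7 off | 7 | 14 |

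The stated two weeks of combination dosing reproduces at both nominal days (14 days each). Both windows also open after 7 combination days, when trametinib is at 1 − 2^(−7/4.5) = 66% of steady state. What differs is time at the assigned navitoclax dose: 7 days against none.

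**2. Pre-dose shortfall after the step-up.** After k days at the new dose N, the share of the step still missing is 0.5^(24k/t½). As a share of the new level it is 0.5^(24k/t½) × (N − 150)/N. The second factor is 0.25, 0.40, 0.50 and 0.54 for 200, 250, 300 and 325 mg. Ranges are for t½ = 15 to 17 h.

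| Before the dose on | Step missing | 200 mg | 250 mg | 300 mg | 325 mg |
|---|---|---|---|---|---|
| Day 8 | 100% | 25% | 40% | 50% | 54% |
| Day 9 | 33-38% | 8.2-9.4% | 13.2-15.0% | 16.5-18.8% | 17.8-20.2% |
| Day 10 | 11-14% | 2.7-3.5% | 4.4-5.7% | 5.4-7.1% | 5.9-7.6% |
| Day 11 | 4-5% | 0.9-1.3% | 1.4-2.1% | 1.8-2.7% | 1.9-2.9% |

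**3. A day-8 biopsy after the morning dose.** At 2 h, well before "Peak concentration was observed approximately 7 hours after dosing" in the solid-tumor study, a one-compartment superposition (my assumption, using the half-lives above and peaks of 6-9 h) puts plasma navitoclax at 84-88% of the new steady-state level at 200 mg, and at 65-74% at 325 mg. That is 35-51% of the step.

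**4. Patients held at 150 mg.** A hold for day-7 platelets leaves 150 mg as the only navitoclax dose received at any biopsy on days 8-14. A permanent hold extends this to the whole window. Either case needs platelets to recover above the biopsy threshold first.

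**5. Schedule C at the late edge.** Trametinib stops after day 14. By day 22, with 7.5-8 days since the last dose, 0.5^(7.5/4.5) to 0.5^(8/4.5) = 31-29% remains. Window days up to day 15, before appreciable washout, number 8 of 15 now. They would be 6 of 13 if the window opened on day 10 and 5 of 12 if it opened on day 11.

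**The case against.** Several points against the concern stand and limit its size.

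- A reader might infer that a day-8 biopsy reflects the lead-in alone. For an escalated patient it normally follows one assigned dose, because navitoclax is taken that morning. Trametinib has also been at its assigned dose for 7 days.
- It is tempting to say that three half-lives (45-51 h) are needed to come within 12% of the new level, so that days 8-10 are affected for everyone. The 12.5% left after three half-lives is a share of the step, not of the level. The day-10 shortfall of about 3-8% is small beside 40% interpatient variability. Levels 1-2, and an RP2D of 150 mg, have no step at all; the documents do not state the RP2D.
- The schedules are aligned on combination days, which is the anchor the protocol names. They are out of line only on days at the assigned navitoclax dose.
- Held patients are those with low platelets, and the biopsy platelet requirement excludes them until counts recover.
- The plan specifies a change per patient. Tabulation by assigned level is a reasonable reading of the stated purpose, but no section lays it down.
- Sections 9.1.2.1 and 9.1.2.2 call these analyses ancillary/exploratory. Escalation and the RP2D rest on DLTs, and Part 2 conclusions on response counts.

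None of this supplies the missing rule. A biopsy with no completed day at the assigned dose remains in window, and nothing in the analysis would identify it.

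**Conclusion.** The gap is real but narrow. It applies to Schedules B and C with assigned navitoclax above 150 mg. For escalated patients it lies mainly on days 8 and 9, two of the 15 window days. By day 10 the remaining shortfall is about 3-8% of the new level. For patients held at 150 mg it lasts through day 14, or throughout the window if the hold is permanent, once counts allow a biopsy. How many biopsies fall in these periods cannot be told from the documents.

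The figures assume first-order approach to steady state, dose proportionality and plasma level as a proxy for tumor exposure. The 2-hour figure also assumes one compartment.

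A reader might go further and infer that an active dose could be dropped because of an early biopsy. The documents do not support that, since no stated decision rule uses these data. This is a minor improvement to a secondary, exploratory endpoint.

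**What to change.** For Schedules B and C with assigned navitoclax above 150 mg, open the on-treatment biopsy window about 2-3 days after the step-up, on day 10 or 11, and leave the closing day no later than now. Make the same change in Sections 2.5.2, 9.1.2.1 and 9.1.2.2 and in the Section 10 calendars.

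In Sections 13.4.1.3 and 13.4.2.1, report and analyse each pair by:

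- actual biopsy day;
- navitoclax dose actually received and number of days at that dose;
- trametinib days on drug and days since the last dose.

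The existing medication diary supplies these. A short fixed lookback, such as the doses taken in the last 3 days, would not serve for trametinib. On Schedule C a day-18 biopsy, about 3.5 days after the last evening dose, would be coded as no trametinib although 0.5^(3.5/4.5) = 58% of the day-14 level remains.

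The cost is a wording change, a few derived variables and 2-3 fewer booking days. On Schedule C those days come from the trametinib-on part of the window, which favours day 10 if scheduling is tight. No treatment dose or clinical rule changes.

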9.1.2.3 Potential risks to patients

The research biopsies performed on this study do carry a low risk of procedure-related complications. To minimize these risks, biopsies will be performed by personnel who are highly-trained and experienced with these procedures (procedures will typically be performed by interventional radiology). In addition, the choice of biopsy site will be based on determination of sites that will have the lowest risk of complication based on sites of disease for the individual patient. Adequate measures will be performed to monitor patients undergoing biopsies. All potential risks associated with these research-purpose biopsies will be discussed verbally and in writing with the patient during the informed consent process upon study enrollment by the study team, and again prior to the procedure by the provider performing the biopsy (typically interventional radiology). Patients will have the choice not to participate in this study if they do not wish to undergo research-related biopsies. Biopsies will only be performed in a given patient if they are not deemed to involve unacceptable risk based on the sites of disease and other concurrent medical conditions. Given the potential for thrombocytopenia associated with navitoclax, biopsies will only be performed if platelet count is >50.000cells/mm3 and stable and coagulation studies (PT/INR and PTT) are in acceptable range, in accordance to institutional guidelines.

9.1.3 Identification of potential predictive biomarkers in pre-treatment tumor tissue

9.1.3.1 Rationale

Given the molecular heterogeneity of KRAS and NRAS mutant cancers, no single therapeutic regimen is expected to be effective in all patients. Therefore, molecular characterization of archived or pre-treatment tumor biopsy tissue for each patient enrolled on this trial will provide a critical opportunity to identify valuable biomarkers to predict which patients are more or less likely to respond to treatment. Initially, these analyses will be exploratory and hypothesisgenerating in nature, but promising biomarker candidates identified in this study can potentially be assessed in future clinical studies evaluating this therapeutic regimen.

Initial laboratory studies evaluating the combination of BCL-XL and MEK inhibition in KRAS mutant cancer cell lines have identified potential biomarkers of sensitivity. For example, our initial studies ([name] et al., 2013) have suggested that KRAS mutant cancers that express markers of epithelial differentiation (e.g. E-cadherin) are more likely to respond to this therapy than cancers expressing markers of mesenchymal differentiation (e.g. vimentin). Thus, E-cadherin and vimentin levels will be assessed by immunohistochemistry in pre-treatment tumor tissues of all patients enrolled on this study and correlated with clinical outcome. Our initial

Version Date: July 22, 2022

work has shown that E-cadherin and vimentin can be readily assessed in formalin-fixed paraffinembedded tissue from KRAS mutant cancer patients ([name] et al, 2013).

9.1.3.2 Procedures and analysis

Pre-treatment tumor tissue for analysis will be obtained either from archival tissue remaining from a patients' prior surgery, diagnostic biopsy, or other procedure performed during routine clinical care. These archival tissue blocks will be obtained from the pathology departments of the Massachusetts General Hospital or Dana Farber Cancer Institute, or will be provided by the pathology department of the institution at which the procedure was performed. Alternatively, tissue derived from the study-related pre-treatment biopsy may also be used for this purpose if necessary. At least 20 unstained slides should be obtained. If a patient is having a tumor biopsy, less than 20 are acceptable with PI approval.

9.1.3.3 Mutational analysis

In depth, mutational analysis will be performed using a 1000 gene next-generation sequencing platform employed as part of standard oncology care at the Massachusetts General Hospital Cancer Center. Mutations in these 1000 cancer-related genes that might affect the likelihood of a patient's tumor to respond to therapy will be correlated with clinical outcome. In addition, further in-depth genomic analyses, including copy number analysis, may be performed on selected specimens.

9.1.3.4 Protein and RNA biomarkers

Selected protein and RNA biomarkers identified in previous (and future) laboratory studies will be analyzed in pre-treatment tissues. Based on initial laboratory studies ([name] et al, 2013) discussed above, E-cadherin and vimentin protein levels will be assessed by immunohistochemistry in formalin-fixed paraffin-embedded tissues. These analyses will be performed using established clinical testing assays by the Clinical Pathology Laboratory at the Massachusetts General Hospital. Analysis of additional protein and RNA biomarkers, such as baseline levels of BIM, BCL-XL, MCL1, and other apoptotic proteins, will also be performed.

